Appendix A – Protocol Registration Form

DEMOGRAPHICS

Patient: Last Name: _____ First Name: _____

MRN: _____ DOB (mm/dd/yy): ____ / ____ / ____

Zip code: _____

Sex: Male Female

Ethnicity (choose one): Hispanic
 Non-Hispanic

Race (choose all that apply): White Black Asian
 Pacific Islander Native American

Marital status: Single Married/Domestic partner
 Separated/Divorced Widowed

Primary Diagnosis: _____

Date of Diagnosis: ____ / ____ / ____

Education: High school or less Some college College Graduate
 Graduate School Doctorate

Health Insurance: Private plan Medicare Medicaid Military None

PROTOCOL INFORMATION

Date of Registration: _____ / _____ / _____

MD Name (last): _____

Date protocol treatment started: _____ / _____ / _____

Informed written consent: YES NO

(consent must be signed prior to registration)

Date Consent Signed: _____ / _____ / _____

PID # (to be assigned by ORIS): _____

Protocol
Registrar
can be
contact by
calling [name]
between
8:30 AM
and 4:00
PM,
Monday –
Friday.

Completed
Eligibility
Checklist
and

Protocol Registration Form must be hand delivered, faxed or e-mailed to the registrar at [name] or [contact].

Appendix B – Subject Eligibility Checklist

Inclusion Criteria (as outlined in study protocol)	Criteria is met	Criteria is NOT met	Source Used to Confirm * (Please document dates and lab results)
Diagnosis of cancer, not including multiple myeloma or lymphoma/leukemia.			
Radiographic evidence* of bone metastases within 8 weeks of study for non-weight bearing sites and 4 weeks for weight bearing sites. The patient must have pain which appears to be related to the radiographically documented metastasis in the opinion of the treating physician, and the decision has been made by the responsible clinician that a course of palliative external beam radiation therapy is appropriate treatment. Multiple sites eligible if they can be included in no greater than 3 treatment sites and not all identifiable lesions will require treatment unless they are painful lesions.			
*This should be one of the following: Plain Film, Bone Scan, PET scan, CT scan, or MRI.			
The involved bone(s) is/are orthopedically stable and not in need of stabilization via either definitive RT, surgical intervention, or both.			
Eligible Treatment Sites Are: Weight bearing sites: 1. pelvis (excluding pubis) 2. femur 3. sacrum and/or sacroiliac joints 4. tibia 5. up to 5 consecutive cervical, thoracic or lumbar vertebral bodies 6. lumbosacral spine Non-weight bearing sites: 5. up to 5 consecutive cervical, thoracic or lumbar vertebral bodies 6. lumbosacral spine 7. up to 3 consecutive ribs 8. humerus 9. fibula 10. radius ± ulna 11. clavicle 12. sternum 13. scapula 14. pubis 15. skull 16. bones of hands or feet If multiple sites are treated, the treatment site is included as weight-bearing if any of the sites include the pelvis, sacrum, femur or tibia.			

A Prospective Randomized Phase II Study of 1 vs 2 Fractions of
 Palliative Radiation Therapy for Patients with Symptomatic Bone Metastasis
 Comprehensive Cancer Center of Wake Forest University (CCCWFU)
 CCCWFU # 01416

Pain score of at least 5 on a scale of 0 – 10 within a week of enrollment OR pain score < 5 with \geq 60 mg of morphine (or equivalent) per day.			
ECOG performance status of 0-3.			
Ability to understand and the willingness to sign an IRB-approved informed consent document.			
Negative pregnancy test at study registration.			
Life expectancy of at least 12 weeks as deemed by the treating oncologist.			
Patients will be eligible for treatment of multiple synchronous osseous sites only if those sites can be included in no more than three treatment sites. For patients with painful metastases that are contiguous but do not fit into the definition of a site listed above, those patients will still be eligible but will be considered to have two treatment sites. For example, a patient with a lesion of T4, T7 and T9 would be eligible but would be considered as two treatment sites since more than five consecutive vertebral bodies would be treated. These lesions could be treated with one field, even though the treatment is coded as two sites.			
Exclusion Criteria (as outlined in study protocol)	Criteria NOT present	Criteria is present	Source Used to Confirm * (Please document dates and lab results)
Previous radiotherapy or palliative surgery to the painful site that is planned for treatment.			
Spinal cord or cauda equine compression/effacement in vertebral metastases with neurologic symptoms other than pain for the lesion that is planned for treatment.			

This subject is eligible / ineligible for participation in this study.

ORIS Assigned PID: _____

Signature of research professional confirming eligibility: _____ Date: _____

Signature of Treating Physician**: _____ Date: _____

* Examples of source documents include clinic note, pathology report, laboratory results, etc. When listing the source, specifically state which document in the medical record was used to assess eligibility. Also include the date on the document. Example: "Pathology report, 01/01/14" or "Clinic note, 01/01/14"

**Principal Investigator signature can be obtained following registration if needed

Appendix C – Race & Ethnicity Verification Form

Thank you so much for helping us to verify your race and ethnicity to ensure the quality of our information. As a brief reminder, the information you provide today will be kept confidential.

1. Are you:

- Hispanic or Latino/a
- Not Hispanic or Latino/a

2. What is your race? One or more categories may be selected.

- White or Caucasian
- Black or African American
- American Indian or Alaskan Native
- Asian
- Native Hawaiian or Other Pacific Islander
- Other, Please Specify: _____

Internal use only:

Name: _____ MRN#: _____

Was the self-reported race and ethnicity of the participant verified at the time of consent?

Yes No

Was a discrepancy found? Yes No

If yes, please provide what is currently indicated in the EMR:

Ethnicity: _____

Race: _____

Additional comments: _____

Appendix D – Mandatory DSMC SAE Reporting Guidelines

Data and Safety Monitoring Committee (DSMC) Serious Adverse Event (SAE) Notification SOP	Date: 02/11/2021
Mandatory DSMC SAE Reporting Requirements in WISER	

This document describes reporting requirements of adverse events from **WFBCCC Investigator Initiated interventional trials to the Data and Safety Monitoring Committee (DSMC)**. A trial is considered a **WFBCCC Investigator Initiated interventional trial** if the following criteria are met:

- 1) The Principal Investigator (PI) of the trial is a member of a department at the Wake Forest University Baptist Medical Center.
- 2) WFBCCC is considered as the primary contributor to the design, implementation and/or monitoring of the trial.
- 3) The trial is designated as “Interventional” using the Clinical Research Categories definitions provided by the NCI in the Data Table 4 documentation.
(<https://cancercenters.cancer.gov/GrantsFunding/DataGuide#dt4>)

There are two distinct types of WFBCCC Investigator Initiated interventional trials based on where patient enrollment occurs. These include:

- 1) Local WFBCCC Investigator Initiated interventional trials defined as trials where **all patients are enrolled from one of the WFBCCC sites**. These include the main outpatient Cancer Center clinics (located in Winston-Salem) as well as WFBCCC affiliate sites located in Bermuda Run (Davie Medical Center), Clemmons, Lexington, High Point, or Wilkesboro.
- 2) Multi-Center WFBCCC Investigator Initiated interventional trials defined as trials where patients are enrolled from other sites in addition to WFBCCC sites.

There are three types of trials that are included in this category:

- a. Trials sponsored by the NCI Community Oncology Research Program (NCORP) that are conducted at multiple sites where the PI is a member of a department at the Wake Forest University Baptist Medical Center.
- b. Trials sponsored by Industry that are conducted at multiple sites and the PI is a member of a department at the Wake Forest University Baptist Medical Center.
- c. Trials sponsored by WFBCCC that are conducted at multiple sites and the PI is a member of a department at the Wake Forest University Baptist Medical Center.

All Adverse Events (AEs) and Serious Adverse Events (SAEs) that occur on any patients enrolled on WFBCCC Investigator Initiated Interventional trials must be entered into the WISER system. The only exception to this requirement is for patients enrolled on NCORP trials at non- WFBCCC sites. AEs and SAEs for NCORP patients enrolled at WFBCCC sites must be entered into the WISER system. Once these AEs and SAEs are entered in WISER, certain actions must be taken regarding the reporting of specific Adverse Events to the DSMC.

All Adverse Events that occur during protocol intervention (defined below) and are coded as either 1)

unexpected grade 4, 2) unplanned inpatient hospitalization > 24 hours (regardless of grade), or grade 5 (death) must be reported to the DSMC using the SAE console in WISER.

A research nurse or clinical research coordinator when made aware that an adverse event meets one of the above criteria has occurred on a WFBCCC Investigator Initiated interventional trial, is responsible for informing a clinical member of the DSMC by phone (or in-person) about the adverse event. The nurse/coordinator should contact the treating physician prior to calling the DSMC clinical member to obtain all details of the SAE, as well as all associated toxicities to be recorded along with the SAE. In addition, this nurse or coordinator is responsible for entering the adverse event information into the SAE console in WISER. Once the adverse event has been entered into the SAE console an email informing the entire DSMC will be generated.

THESE REPORTING REQUIREMENTS APPLY TO any staff member on the study team for a WFBCCC Institutional Interventional trial. Ultimately, the protocol PI has the primary responsibility for AE identification, documentation, grading and assignment of attribution to the investigational agent/intervention. However, when an AE event as described above is observed, it is the responsibility of the person who observed the event to be sure that it is reported to the DSMC.

What is considered during protocol intervention?

During protocol intervention is considered to be the time period while a patient is on study treatment or during the time period within 30 days of last study treatment (even if patient begins a new (non-study) treatment during the 30 days). This window of 30 days should be the standard window to be used in all protocols unless a specific scientific rationale is presented to suggest that a shorter window can be used to identify events. If it is a trial sponsored by Industry and the sponsor requires a longer window for monitoring of SAEs, then the longer window of time specified by the sponsor should be followed.

What is considered as an Unexpected Grade 4 event?

Any grade 4 event that was not specifically listed as an expected adverse event in the protocol should be considered as unexpected. A grade 4 adverse event can be considered to be unexpected if it is an event that would not be expected based on the treatment being received or if it is unexpected based on the health of the patient. In either case, if there is any uncertainty about whether a grade 4 adverse event is expected or unexpected it should be reported to DSMC.

DSMC notification responsibilities of the person (e.g., nurse) handling the reporting/documenting of the SAE in WISER:

1. Make a phone call (or speak in person) to the appropriate clinical member of the DSMC according to the schedule as listed below (page if necessary).
2. Enter a new SAE into the SAE module that is located in the Subject>> CRA Console inWISER WITHIN 24 HOURS of first knowledge of the event. Information can be entered and saved, but the DSMC members will not be notified until a date is entered into the DSMC Notification Date Field. This will ensure that all persons that need to be made aware of the event (i.e., PI, study team members and DSMC members) will be notified; remember to file a copy of the confirmation.
3. Document that the appropriate person(s) on the DSMC has been contacted. Indicate the name of the DSMC clinician that was contacted and the date and time contacted in the Event Narrative field in the SAE console of the particular subject.
4. Document whether or not the protocol should be suspended based on the discussion with the DSMC clinician. This is the major function of the email notification. Enter whether the protocol

should be suspended in the Event Narrative Field.

5. Follow up/update the clinical member(s) of DSMC regarding any new developments or information obtained during the course of the SAE investigation and reporting process.

[figure not shown]
Elements needed to complete the SAE form in the Subject Console in WISER (see Screen Shot 3):

1. Event Date
2. Reported Date
3. Reported by
4. If Grade 5, enter Death Date
5. If Grade 5, enter Death occurred: within 30 days
6. Event Narrative: Brief description (include brief clinical history relevant to this event, including therapies believed related to event). Begin narrative with the DSMC clinician who was notified and Date/Time notified. In addition, state attribution by DSMC clinician as either "Unrelated", "Unlikely", "Possibly", "Probably", or "Definitely". Always include the following here:
 - i. DSMC clinician name, date/time contacted and comments
 - ii. Date of last dose before the event
 - iii. Is suspension of the protocol needed? Y/N
7. Treating Physician comments
8. PI comments, if available
9. Protocol Attribution after discussion with DSMC clinician
10. Outcome (Fatal/Died, Intervention for AE Continues, Migrated AE, Not Recovered/Not Resolved, Recovered/Resolved with Sequelae, Recovered/Resolved without Sequelae, Recovering and Resolving)
11. Consent form Change Required? Y/N
12. SAE Classification ***This is required in order for the email notification to be sent***
13. Adverse Event Details – Enter all details for each AE associated with the SAE.
 - a. Course start date
 - b. Category
 - c. AE Detail
 - d. Comments
 - e. Grade/Severity
 - f. Unexpected Y/N
 - g. DLT Y/N
 - h. Attributions
 - i. Action
 - j. Therapy
 - k. Click ADD to attach the AE Detail to the SAE.
14. Enter Date Notified DSMC -- ***This is required for the email notification to be sent***

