For patients with a pain score >4 in the treated area at the 3 and 6 month follow-up, imaging (plain film, CT, bone scan, MRI) is recommended to assess for bone stability and pathologic fractures. Imaging should correlate with other imaging ordered by other treating physicians when possible. Coordination of all treatment and imaging should be collaborative to ease patient burden.

We will also include the following psychosocial measures at baseline and again at 3 and 6 months:

- European Organization for Research and Treatment of Cancer (EORTC) QLQ-C15-PAL
- Patient Satisfaction with Cancer Care (11)
- Perceived Stress Scale (12)
- Social Support (13)

Measurement of Treatment-Related Toxicities: Adverse events will be evaluated by the NCI Common Terminology Criteria for Adverse Event (CTCAE), v. 4.0. (14). Because of the patient population as well as the treatment, emphasis will be placed on gastrointestinal (GI disturbance, esophagitis, diarrhea, nausea, and vomiting), hematological (low blood counts or bleeding), spinal (bone fracture, compression fracture, insufficiency, or myelitis), and pulmonary toxicities (pneumonitis). However, all adverse events recorded by clinical research coordinators will be analyzed. Given the variety of non-protocol related treatment, toxicity will be assessed at 30 days after protocol treatment, as per DSMC requirements. These will be documented in Appendix I.

Focused Late AE Assessments: At 2, 3 and 6 months post-treatment, a focused AE assessment dependent upon the specific body area treated will be performed. These will be documented in Appendix I. Specific AEs to be collected will include the following:

- a) Fistula formation
 - a. Abnormal opening in the passageway from mouth to stomach (esophagus), bowels or bladder
- b) Scarring of the small or large bowel resulting in a blockage in the bowel that would require treatment
- c) Fracture of the bone within the radiotherapy treatment field (Fractures may require surgical treatment to prevent permanent disability).
- d) Temporary or permanent damage to the spinal cord, resulting in:
 - a. Skin sensations, such as burning, prickling, itching, or tingling
 - b. Muscle weakness causing inability to walk (paralysis)
 - c. Decreased ability or loss of ability to move a body part or to hold urine or control a bowel movement

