6.0 Treatment Plan

6.1 Study-Related Activities

	Screening/ Baseline ^a	Pre-Treatment ^h	At Each Treatment	1 Month Post Treatment Completion ^{f,g}	2 Months Post Treatment Completion ^{f,g}	3 Months Post- Treatment Completion ^{f,g}	6 Months Post- Treatment Completion ^{f,g}
Informed Consent	X						
Demographics: age, gender, education, health, insurance, marital status	X						
Medical history, tumor characteristics	X						
Performance Status (ECOG)	X					X	X
B-HCG ^b	X						
Blood Collection (optional)		X				X ^{f,i}	
Nutritional status, BMI _i	X		X			X	X
Vital Signs	X					X	X
Radiologic assessment	X ^c					X ^{e,m}	X ^{e,m}
Patient Questionnaires ^d		X				X	X
Concomitant Medications	X		X	X	X ^k	X ^k	X ^k
Adverse event evaluation			X	X	X ^j	X ^j	X ^j
NRPS Pain Scale	X			X ^g	X ^g	X ^g	X ^g

a. Pre-study requirements listed in table must be completed **within** 14 days prior to registration unless otherwise noted.

b. Serum pregnancy test (women of childbearing potential).

c. Within 8 weeks of registration for non-weight bearing sites and 4 weeks for weight bearing sites

d. See Appendix G.

e. Imaging ordered by the treating physician according to the standard of care, only if indicated. CT scan is not required to be performed for study purposes at follow up, but any CT scans obtained as standard of care will be used for purposes of reviewing changes in cortical thickness as an exploratory aim.

f. To be completed 3-6 weeks from final treatment date (1 month visit), 7-9 weeks from final treatment date (2 month visit), 10-18 weeks from final treatment date (3 month visit) and 20-34 weeks from final treatment date (6 month visit).

g. For patients who are undergoing additional therapy of any kind and are being followed by another treating physician, the follow-up visit can be deferred to that treating physician. Schedule of follow-up may be deferred to that treating physician and activities will be captured when they fall within visit windows. Toxicity (AEs), pain (NRPS), and patient questionnaire can be done over the phone +/- 5 days of said visit.

h. To be completed any time after consent is signed, but prior to treatment. Not needed for registration.

i. Height will be captured at the Pre-Study/Baseline visit only.

j. Focused AE assessment according to those specified in Section 4.3 and outlined in Appendix I (2-, 3- and 6- month assessment).

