6.4 Duration of Follow Up

Given the variety of non-protocol related treatment, toxicity will be assessed at 30 days after protocol treatment as it is anticipated that this would be part of standard of care for such treatment, and per DSMC requirement. For patients not receiving any additional treatment, additional follow-up visits will occur at 3 and 6 months with follow-up radiologic assessment at the discretion of the treating physician if pain score is >4 as such is standard of care for patients who receive the treatment.

For patients who are undergoing additional therapy of any kind and are being followed by another treating physician, follow-up can be deferred to that treating physician. Toxicity and pain can be assessed via chart review and over the phone for these patients at the appropriate study time points. Patients will be followed in this same manner if being treated at an outside facility. Patients who experience adverse events will be followed every 3-6 weeks until stabilization of the adverse event or until 6 months post-treatment, whichever occurs first.

A patient may remain in the study until one of the following criteria applies:

- Patient decides to withdraw from the study, or

- The patient has completed a minimum of 6 months follow-up.
- Patient enters End of Life Hospice Care and will no longer be followed routinely.

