8.3 DSMC SAE Reporting Requirements

The Data Safety Monitoring Committee (DSMC) is responsible for reviewing SAEs for WFBCCC Institutional studies as outlined in Appendix D. All Adverse Events that occur during protocol intervention and are coded as either 1) unexpected grade 4, 2) unplanned inpatient hospitalization \geq 24 hours (regardless of grade), or grade 5 (death) must be reported to the DSMC using the SAE console in WISER.

All WFBCCC Clinical Protocol and Data Management (CPDM) staff members assisting a Principal Investigator in investigating, documenting and reporting an SAE qualifying for DSMC reporting are responsible for informing a clinical member of the DSMC as well as the entire committee via the email notification procedure of the occurrence of an SAE.

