10.0 Data Management

Informed consent document	Wiser
Appendix A: Protocol registration form	Wiser
Appendix B: Subject Eligibility Checklist	Wiser
Appendix C: Race & Ethnicity Verification	Wiser
Appendix D: Mandatory DSMC SAE Reporting Guidelines	Wiser
Appendix E: Baseline data collection form	REDCap
Appendix F: Treatment data collection	REDCap
Appendix G: Patient Questionnaire	REDCap
Appendix H: Numerical Rating Pain Scale (NRPS)	REDCap
Appendix I: Adverse Events	Epic/REDCap
Appendix J: Retreatment Data Form	REDCap
Appendix K: Radiation Induced Bone Changes	REDCap

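### Mandatory DSMC notification stops 30 days after the last fraction, but the focused late-toxicity visits open at day 49, so serious late events in either arm have no mandatory route to the DSMC

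*Combined protocol and SAP*

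**What the plan says.** **The trigger.** Section 8.3 opens its reporting rule with "All Adverse Events that occur during protocol intervention and are coded as either 1) unexpected grade 4", and adds unplanned admissions and deaths. Appendix D repeats the rule and defines the period as time on study treatment or "during the time period within 30 days of last study treatment". It makes 30 days the standard for all protocols "unless a specific scientific rationale is presented to suggest that a shorter window can be used", and allows a longer window where an industry sponsor asks for one.

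**The late assessments.** Section 4.3 states: "At 2, 3 and 6 months post-treatment, a focused AE assessment dependent upon the specific body area treated will be performed". The events are fistula, bowel scarring with obstruction, fracture within the treatment field, and temporary or permanent cord damage. The late page of the Appendix I log also lists bowel perforation. Footnote f of the Section 6.1 calendar sets the visits at weeks 7–9, 10–18 and 20–34 after the final treatment.

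**Recording.** Under Appendix D, all AEs and SAEs on these trials "must be entered into the WISER system", with no time limit in that sentence. An entry in the SAE console emails the committee once a DSMC notification date has been filled in. Section 10 assigns "Appendix I: Adverse Events" to Epic/REDCap.

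**Follow-up of events.** Section 6.4 follows patients with adverse events "until stabilization of the adverse event or until 6 months post-treatment, whichever occurs first".

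**Interim look.** Section 11.6 plans one analysis, at 50 patients: a futility test on re-treatment with no safety criterion.

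**The concern.** The harms that Section 4.3 singles out for focused late follow-up are assessed in that way only after the period in which the DSMC must be told about them. Followed as written, the plan makes notification of the same serious event depend on its date of onset alone.

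Objective 2.2.3 asks whether two fractions increase toxicity, and the late events are a large part of the answer. Appendix D gives the DSMC the power to suspend the trial pending investigation. With nothing that obliges the study team to notify a late event, and no late-toxicity listing at the interim, the committee may learn of such events only if someone chooses to tell it. Enrolment would continue meanwhile.

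**Working it through.** The plan states no figure to reproduce here. The check compares the reporting window with the visit windows.

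**Inputs.** Window end: day 30 after last treatment (Appendix D). Visit windows: Section 6.1, footnote f. Six months is taken as 26 × 7 = 182 days. Accrual: 3 patients a month (Section 11.4).

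**Step 1: visits against the window** (days = weeks × 7; gap = opening day − 30)

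| Visit | Weeks | Days | Gap to day 30 |
|---|---|---|---|
| 1 month (general AE evaluation) | 3–6 | 21–42 | opens 9 days before, may run 12 days past |
| 2 months (focused) | 7–9 | 49–63 | 19 days after |
| 3 months (focused) | 10–18 | 70–126 | 40 days after |
| 6 months (focused) | 20–34 | 140–238 | 110 days after |

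All three focused visits open after mandatory notification has closed.

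**Step 2: share of follow-up outside the window.** (182 − 30)/182 = 152/182 = 84%. If the last visit is at week 34, (238 − 30)/238 = 208/238 = 87%.

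**Step 3: is it the date alone that removes the event?** Section 8.1 lists the expected effects. Fistula, bowel obstruction, fracture and cord damage are not among them, and Appendix D treats an unlisted grade 4 event as unexpected. A grade 4 cord injury on day 29 must therefore be notified. The same injury on day 60 meets every condition except the window. The rule turns on when the event occurs, so one with onset before day 30 that is found at a later visit remains reportable. The gap is onset after day 30.

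**Step 4: does another provision close the gap?**
- WISER entry (Appendix D) applies without a time limit, but entry is not notification. The email waits for a DSMC notification date, and nothing requires that date for an event outside the window.
- IRB reporting (Section 8.4) covers unanticipated problems within 7 calendar days and has no 30-day limit. It goes to a different body.
- The interim analysis (Section 11.6) tests re-treatment only.
- Section 10 and Appendix D name different systems for adverse events, so the WISER step itself needs to be made clear.

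**Step 5: enrolment meanwhile.** At 3 patients a month, 3 × 152/30.44 = about 15 patients are enrolled over the 152 days between day 30 and day 182 of any one patient. This describes the pace of accrual. It does not count missed events.

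**Step 6: the 6.4 limit.** Section 6.4 ends event follow-up at 6 months, but the 6-month visit may fall up to day 238, which is 238 − 182 = 56 days later. The two passages do not say what applies to an unstable event found in that interval.

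**The case against.** The strongest defence is that the 30-day window was chosen openly. Sections 4.3 and 6.4 tie the 30-day toxicity assessment to the variety of non-protocol treatment, and Appendix D makes 30 days the institution's standard. Systemic therapy may change and sites may be re-irradiated, so late events are harder to attribute. This stands as a reason for caution in interpretation. It does not explain why a serious late event should go unnotified: the log already has an attribution column, and randomisation supplies a comparison group.

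Several stronger readings are tempting, and the documents do not support them:

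- **That late events have no route at all to the DSMC.** WISER entry is required, console notification is available, and the IRB route is separate. Only a mandatory DSMC trigger is missing. Appendix D is also a notification procedure, not a committee charter, and parts of it are absent from the public text, so one cannot conclude that the DSMC never reviews late toxicity.
- **That all the named harms are first sought at 2 months.** Section 4.3 emphasises fracture and myelitis in the general toxicity evaluation, which the calendar schedules at each treatment and at 1 month. The 1-month log does not preprint them, but they are within scope. Fistula and bowel obstruction are first prompted at 2 months.
- **That the gap concerns the 16 Gy arm alone.** The window is the same in both arms.
- **That the log's reporting codes, which omit the DSMC, prove the gap.** The 1-month log uses the same codes, although many of its events fall within the mandatory window.
- **That a probability of a missed report can be given.** No late-event rate is stated, and a usable one would have to be limited to onset after day 30.
- **That the 6-month limit in Section 6.4 should be removed.** That would change a patient follow-up rule and add follow-up. The documents support only reconciling it with the visit window.

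**Conclusion.** The point holds in a limited form. Mandatory DSMC notification covers treatment plus 30 days. The three focused late assessments open 19, 40 and 110 days after it ends, and 84% of a 182-day follow-up lies outside it. No provision in the available text requires a serious event with onset after day 30, in either arm, to be notified to the DSMC.

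This follows from the rules as written and needs no assumed event rate. It rests on reading Section 8.3 and Appendix D as the complete mandatory route. If a separate charter or standing procedure sends late events to the committee, the remedy reduces to citing it. The primary efficacy analysis is unaffected. This is an inexpensive improvement to safety oversight that is worth making.

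**What to change.** 1. In Section 8.3, state that for this trial the late events listed in Appendix I (fistula, bowel obstruction, bowel perforation, fracture, cord damage), in either arm, that are grade 4–5 or lead to unplanned hospitalisation are reported to the DSMC through the WISER SAE console up to the 6-month visit.
2. In Section 11.6, add a by-arm listing of late events for the DSMC at the 50-patient interim.
3. Reconcile Section 10 with Appendix D, so that it is clear how Appendix I data held in Epic/REDCap reach WISER.
4. Reconcile the 6-month limit in Section 6.4 with the week 20–34 visit window.

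Items 1 to 3 need protocol wording, a few extra console entries and one listing. The events are already collected at scheduled visits, so no visit or procedure is added. The downside is slightly more DSMC reporting, on events whose attribution is less certain because of non-protocol therapy.
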